Genetic (DNA) evaluation (where local regulations permit)		X																	Whole blood will be collected only from participants who consent to participate in the optional DNA analysis. The pharmacogenomic (DNA) sample should be collected at the specified time point; however, if necessary it may be collected later without constituting a protocol deviation.
Efficacy (clinical as	ssessments/C	D-re	lated	healt	hcare	utili	zation	/PRC	Os)										
Electronic daily diary by site staff		x	х	х	х	х	х	x	x	x	x	х	х	х	х		х	х	Remind participant to complete electronic daily diary for the length of the study. The daily diary includes patient-reported data for the CDAI (includes PRO-2 components).

Study Procedure	Screening Visit (within 5 weeks prior to Week 0)								Stu	dy vis	sits (V	Veek)ª	1				Flare visit a,c	Early Termination visit ^{a,d}	Notes
		0	8	16	24	32	40	48	64	80	96	112	128	144 Final dose	152 Final efficacy	156 Final safety			
CDAI assessments		x	x	х	x	x	х	x	x	x	x	X	Х	X	X		X	X	For calculation of CDAI. The hematocrit value obtained during screening will be used to calculate CDAI at Week 0. For all other visits, the hematocrit value from the most recent study visit available will be used to calculate the CDAI.
Weight (component of CDAI)	Х	X	X	х	х	X	x	X	X	x	x	х	Х	х	Х		X	х	In kilograms (kg)
Fistula assessment	X	X	X	X	X	X	X	X	X	X	X	X	X	X	X		X	X	

Study Procedure	Screening Visit (within 5 weeks prior to Week 0)								Stu	dy vis	sits (V	Veek) ^a	ı				Flare visit	Early Termination visit ^{a,d}	Notes
		0	8	16	24	32	40	48	64	80	96	112	128	144 Final dose	152 Final efficacy	156 Final safety			
Video ileocolonoscopy with biopsy and histology					Xf			X^{f}							X f		X	X f	Week 24 procedure is optional, at the discretion of the investigator with agreement of the participant and should be performed ± 14 days from the scheduled visits. Week 48 procedure should be performed between Weeks 48 to Week 51. In the event procedure performed on the day of the designated visit or the 7 days prior, CDAI scores should be calculated using the proximate 7 days that were not impacted by the ileocolonoscopy or its preparation. Refer to the biopsy manual for details on the biopsy sample collection.
Stool sample (fecal calprotectin)	х	х			х		х	х		х			х		х		х		Week 0: Not required if sample already collected during screening is within 2 weeks of the Week 0 visit.

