A Week 48 video ileocolonoscopy will be performed between Weeks 48 and 51 and participants with endoscopic recurrence confirmed by a central reader will cross over to open-label treatment with guselkumab SC induction. An optional video ileocolonoscopy can be performed at Week 24 and cross over will occur at the discretion of the principal investigator if there is only endoscopic recurrence without disease recurrence. If participants meet criteria for disease recurrence after Week 8 they will also cross over to open-label treatment.

Participants who discontinue study intervention early will return for an early termination visit at least 12 weeks after study intervention discontinuation, which will also serve as their final safety visit. This visit will include a video ileocolonoscopy at the time of discontinuation, except those participants who have already had demonstrated endoscopic recurrence in a study ileocolonoscopy.

Database Locks and Maintenance of the Blind

The first database lock (DBL) is the main study DBL. It will occur when all participants have completed the Week 48 visit assessments, or have terminated study participation prior to Week 48, and will include all assessments performed as of that date (even those beyond Week 48). The final DBL will occur after the last participant completes the final safety visit at Week 156. Additional DBLs may be added between Weeks 48 and 156, as warranted.

The study blind will be maintained for the investigative sites, site monitors, and study participants until after the final participant has completed their Week 156 visit. In the event of an emergency, the investigator may also unblind a participant's treatment if such knowledge would change the participants' clinical care. The sponsor will remain blinded to the original treatment assignments until after the main study DBL has occurred.

Study Length

After the screening period, the total study duration is 156 weeks, with the final dose of study intervention given at Week 144 and the final efficacy visit at Week 152 followed by the final safety visit at Week 156. The end of the study is defined as when all participants have completed the Week 156 visit assessments, or have terminated study participation prior to Week 156 and had their last follow-up assessment (12 weeks after the last dose of study intervention or at early termination visit).

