Accrual time used here is 18 months, total time used here is 30 months. It is expected median follow-up time available at the time of, and thus incorporated in, the main database lock is approximately 18 months. Assuming non-uniform accrual pattern: 25% of participants will be enrolled in the first 6 months, 35% of participants will be enrolled in the next 6 months, and 40% will be enrolled in the last 6 months. Assuming dropout rate is 15% annually. Average duration of follow-up is expected to be approximately 20 months.

Analysis Sets	Description
Randomized	The randomized analysis set includes all participants who were
	randomized in the study.
Full Analysis Set (FAS)	All randomized participants.
	Participants in the FAS will be analyzed according to their randomized study intervention regardless of the study intervention they actually received.
Safety Analysis Set	All randomized participants who receive at least 1 dose of study intervention.
	Participants in the Safety Analysis Set will be analyzed according to the study intervention they actually received.
Pharmacokinetics Analysis Set	All randomized participants who receive at least 1 dose of study intervention and have at least one valid blood sample drawn postbaseline for PK analysis.
	Participants in the PK Analysis Set will be analyzed according to the study intervention they actually received.
Immunogenicity Analysis Set	All participants who received at least 1 dose of study intervention and have appropriate samples for anti-drug antibody detection.
	Participants in the Immunogenicity Analysis Set will be analyzed according to the study intervention they actually received.

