5.5. Other Endpoint(s) Analysis

5.5.1. Definition of Endpoints

- Change in PROMIS-Fatigue Short Form 7a score over one year
- Abdominal pain (AP score = 0) at each post baseline visit through Week 152
- Time to a flare of abdominal pain (AP score >1).
- Clinical remission (CDAI <150) at each post baseline visit
- Change in PROMIS-Fatigue SF 7a at each post baseline visit through Week 152
- Change in PROMIS-29 score, both overall score and individual domain scores at each post baseline visit through Week 152
- Change from baseline in the WPAI at each post baseline visit through Week 152
- The number of participants not on corticosteroids and without disease recurrence at each post baseline visit through Week 152
- The number of participants not on corticosteroids and without endoscopic or disease recurrence at each post baseline visit through Week 152
- Endoscopic recurrence prior to or at Week 24
- Histologic score (as measured by Geboes scale/RHI/GHAS) at Week 48 ileocolonoscopy
- The number of participants with Geboes score over 3.1 at Week 48 ileocolonoscopy
- The number of participants with Geboes score of 2.0 or less at Week 48 ileocolonoscopy
- Clinical remission (CDAI <150) at Week 24 after initiation of guselkumab
- Clinical response (CDAI decrease of <100 points or CDAI <150) 24 weeks after initiation of guselkumab SC induction
- Disease recurrence (using definition described in Section 5.4.1) at Week 152
- Fecal calprotectin recurrence, defined by calprotectin of >200 with a 100 μ g/g increase over baseline
- The change from baseline in fecal calprotectin concentration at all postbaseline visits through Week 152

- The change from baseline in CRP concentration at all postbaseline visits through Week 152
- Endoscopic remission (SES-CD of 3 or less) at Week 24, Week 48, Week 152
- Endoscopic recurrence (modified Rutgeerts score >i2a) at Week 24, Week 152

PRO Instruments

• PROMIS-29

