5.5.2. Analysis Methods

Unless otherwise specified, the exploratory endpoints listed and defined in Section 5.5.1 will be analyzed based on the FAS according to the randomized intervention group regardless of the intervention actually received.

All exploratory endpoints will be tested regardless of the significance of the primary and secondary endpoints; the testing of these endpoints will not be controlled for multiplicity. Nominal p-values will be presented.

Descriptive statistics (ie, N, mean, median, SD, IQ range, minimum, and maximum) will be used to summarize continuous variables. Frequency counts and percentages will be used to summarize categorical variables. Graphical data displays (eg, line plots) may also be used to summarize the data.

Binary Endpoints

The intercurrent events captured for binary endpoints specified in Section 5.3.2 will be applied to each of the above binary endpoints. Participants with ICEs in categories 1-4 will be considered to have unfavored outcome. For participants experiencing an ICE 5 and ICE 6, their observed values will be used, if available.

Participants with any missing data for an endpoint after accounting for the ICEs will be imputed as having unfavored outcome. Binary endpoints will be summarized with the number and frequency of participants who achieve the endpoint by treatment group. Treatment comparisons will be performed using CMH chi-square test stratified by clinical remission status at baseline (CDAI < 150, CDAI \ge 150), region (North America, Western Europe, rest of world) and number of prior surgeries (1 surgery versus > 1 surgery, with the qualifying surgery counting as 1 surgery). In case of rare events, the Fisher's exact test will be used for treatment comparisons.

Time-to-event Endpoints

The ICEs captured for time-to-event endpoints specified in Section 5.4.1 will be applied to each of the above time-to-event endpoints. Participants with ICEs in categories 1-3 will be considered to have unfavored outcome. For participants experiencing an ICE 4 and ICE 5, their observed values will be used, if available.

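### The optional Week 24 ileocolonoscopy meets a missing-equals-unfavored rule, so compliant participants who were not scoped count as Week 24 failures in three exploratory endpoints

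*SAP*

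**What the plan says.** The Schedule of Activities in Protocol 1.3 notes: "Week 24 procedure is optional, at the discretion of the investigator with agreement of the participant". SAP 1.2.1 repeats this: "An optional video ileocolonoscopy can be performed at Week 24". Footnote f to the schedule lets an ileocolonoscopy done for a flare within 12 weeks of the visit stand in for the scheduled one.

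SAP 5.5.1 lists three binary endoscopic endpoints with a Week 24 time point:

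- "Endoscopic recurrence prior to or at Week 24"
- "Endoscopic recurrence (modified Rutgeerts score >i2a) at Week 24, Week 152"
- "Endoscopic remission (SES-CD of 3 or less) at Week 24, Week 48, Week 152"

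SAP 5.5.2 says that, unless otherwise specified, these endpoints "will be analyzed based on the FAS according to the randomized intervention group regardless of the intervention actually received". The full analysis set is everyone randomized. Participants with intercurrent events (ICEs) 1-4 are failures by definition: CD-related surgery, a prohibited medication change, stopping for lack of efficacy or worsening disease, or cross over. After that step, the missing-data rule is "Participants with any missing data for an endpoint after accounting for the ICEs will be imputed as having unfavored outcome". Arms are compared by a stratified Cochran-Mantel-Haenszel (CMH) test with nominal p-values. Nothing elsewhere restricts the Week 24 denominator, sets a different rule for it, or says that an optional procedure not done is anything other than missing.

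The primary endpoint is handled differently. Its Week 48 endoscopy is scheduled for all, and SAP 5.3.3.1 uses multiple imputation for missing results.

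**The concern.** Counting missing as failure is a common choice when an assessment was due and its absence may signal a poor outcome. Here the absence is built into the design. A participant can follow the protocol exactly, have no Week 24 procedure, and be scored as recurrent or not in remission for that reason alone.

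Two things are at stake. First, the reported Week 24 recurrence rates would mix disease seen at endoscopy with procedures that nobody required, and the treatment difference would shrink as uptake falls. Second, the decision to scope is made after randomization by investigator and participant. If it differs between arms, the rule turns that difference into an apparent treatment effect, or cancels a real one.

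**Working it through.** **1. The plan's own figure.** The documents give no rate or power for Week 24. For Week 48, Protocol Table 5 states 97.7% power for 50% v 30% with 185 per arm and two-sided alpha 0.05. With the pooled normal approximation:

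- Null standard error: √(2 × 0.40 × 0.60 / 185) = 0.0509
- Alternative standard error: √((0.25 + 0.21) / 185) = 0.0499
- z = (0.20 − 1.96 × 0.0509) / 0.0499 ≈ 2.01, so power is 97.8%

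This reproduces the stated figure, and the same method is used below.

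**2. One participant under the rules.** Take a participant with no Week 24 endoscopy, no flare endoscopy, no ICE, and a centrally read i0 at Week 48.

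- Primary endpoint, recurrence by Week 48: no recurrence, as observed.
- Exploratory endpoint, recurrence by Week 24: missing, so recurrence.

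An event by Week 24 is also an event by Week 48, so the two records conflict. The other two endpoints refer to status at Week 24. Poor status then and good status at Week 48 is not a contradiction, although the Week 24 value is still invented.

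**3. Equal uptake.** Let u be the share scoped at Week 24 and p the true recurrence rate. Assume that u is the same in both arms and unrelated to outcome. For simplicity, ignore flare substitution and ICEs, which settle some participants' status without the missing-data rule.

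- Reported recurrence = u·p + (1 − u) = 1 − u(1 − p)
- Reported difference = u × (p for placebo − p for guselkumab)
- Share of reported recurrences that are imputed = (1 − u) / [1 − u(1 − p)]

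Assume that the Week 48 planning rates, 50% and 30%, also hold at Week 24. With 185 per arm:

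| Uptake | Placebo v guselkumab, reported | Difference | Power under the rule | Imputed share, placebo / guselkumab | Power, observed only (n per arm) |
|---|---|---|---|---|---|
| 90% | 55% v 37% | 18 points | 94% | 18% / 27% | 96% (166) |
| 75% | 62.5% v 47.5% | 15 points | 83% | 40% / 53% | 93% (139) |
| 50% | 75% v 65% | 10 points | 56% | 67% / 77% | 80% (92) |
| 25% | 87.5% v 82.5% | 5 points | 27% | 86% / 91% | 50% (46) |

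The factor u does not depend on the rates chosen. The levels do. The only 24-week placebo rate in Protocol Table 4 is 64%. At 50% uptake that would be reported as 1 − 0.5 × 0.36 = 82%.

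For SES-CD remission with true rate r, the reported rate is u·r. It is pushed toward zero, and the difference shrinks by the same factor.

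**4. Unequal uptake.**

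- No true effect, 50% in both arms, with 30% of placebo and 50% of guselkumab scoped. Placebo is 1 − 0.3 × 0.5 = 85% and guselkumab is 1 − 0.5 × 0.5 = 75%. This is a false 10-point benefit, with a 67% chance of p < 0.05.
- True rates 50% v 30%, with 50% of placebo and 35.7% of guselkumab scoped. Placebo is 1 − 0.5 × 0.5 = 75% and guselkumab is 1 − 0.357 × 0.7 = 75%. The true effect disappears.

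**The case against.** The best defence is that the damage is narrow. The endpoints are exploratory, outside the testing hierarchy, and carry nominal p-values. SAP section 1 says that only four participants were enrolled and that the planned analyses no longer apply. All of this stands: no reported test and no primary or secondary conclusion is touched.

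Four stronger readings are tempting, and the documents do not support them.

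- A reader might infer that everyone without a Week 24 endoscopy is misclassified. A flare ileocolonoscopy can substitute under footnote f, and participants with ICEs 1-4 are failures by the estimand, not by the missing-data rule.
- A reader might infer that the endpoints measure only who was scoped. That depends on uptake, which is not stated. Observed scores still count, and at 90% uptake they supply most of the reported recurrences.
- A reader might infer that the endoscopic-efficacy objective cannot be answered. That objective is also assessed at Weeks 48 and 152, where the procedure is scheduled.
- A reader might compute an uptake below which Week 24 recurrence exceeds the planned Week 48 rates. Any such threshold reflects the rates assumed. With the 64% figure from Table 4, placebo exceeds 50% even at full uptake.

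It could also be said that the rule is merely conservative. With equal uptake it does bias toward no difference. With unequal uptake it need not, as step 4 shows.

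**Conclusion.** The point holds for the three exploratory Week 24 endoscopic endpoints in the plan as designed. It is a stated rule that gives a wrong result, not a missing detail: applied as written, it scores compliant participants with no endoscopy, no substitute and no ICE 1-4 as failures. The contradiction with the primary endpoint is confined to recurrence by Week 24.

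The difference shrinks to u times its true value only if uptake is equal in both arms and unrelated to outcome. If uptake differs by arm, the error can go either way. Uptake and the Week 24 rates are assumptions throughout, so the table shows a range and not a forecast. The Week 48 and Week 152 endpoints, and all primary and secondary analyses, are unaffected.

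**What to change.** In SAP 5.5.2, exempt the Week 24 endoscopic endpoints from the missing-equals-unfavored rule and state instead:

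- Report them descriptively among participants with a centrally read Week 24 ileocolonoscopy, or a flare ileocolonoscopy that substitutes under footnote f.
- Give the number and percentage scoped in each arm.
- Show participants with ICEs 1-4 by Week 24 as a separate count. Adding ICE failures who were not scoped to the observed-endoscopy denominator, while leaving out other participants who were not scoped, would bias the recurrence rate upward.
- Give no full-analysis-set p-value, and label the estimate as coming from a selected subset.

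Multiple imputation, as used for the primary endpoint, is a possible alternative. It would rest on a missing-at-random assumption that is hard to defend if suspicion of disease drives the choice to scope.

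The cost is SAP wording only. The downside is a smaller, selected denominator for exploratory endpoints.

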1.2. Study Design

1.2.1. Overall Design

This is a Phase 3, multicenter, randomized, placebo-controlled, prospective double-blind study designed to evaluate the efficacy and safety of guselkumab in preventing the recurrence of active CD in patients who have recently undergone a surgical resection for CD. A diagram of the study design is provided in Section 1.2.2, Schema.

The target population is male or female participants (minimum age 18) with a diagnosis of CD who have a qualifying surgery (eg, ileocolonic resection) a maximum of 49 days before randomization. Participants will be excluded if they have a short segment of bowel affected (ie, less than 10 cm) for fibrostenotic disease and they had their first surgery more than 10 years after diagnosis of CD. There is no requirement that participants have failed prior biologics.

Participants will have a baseline CDAI <200 and will be eligible regardless of prior biologic use. Participants who are low risk for recurrent CD (ie, participants whose qualifying surgery was their first in >10 years since their diagnosis of CD and was performed for fibrostenotic stricturing disease involving <10 cm of the intestine) will be excluded. Participants must be able to undergo randomization no later than 49 days after surgery.

A target of approximately 370 participants will be enrolled from approximately 150 sites. The target population consists of participants with CD who have undergone a recent (\leq 49 days) ileocolonic resection with ileocolonic anastomosis for CD, without evidence of active disease postoperatively. Participants must not have had their qualifying surgery for the purpose of resecting known dysplasia.

Randomization will occur in a 1:1 ratio with participants receiving either:

- Arm 1 (Guselkumab): Guselkumab ^{CCI} at Week 0 and then ^{CCI} at Week 8, then ^{CCI} thereafter through the end of the total study period.
- Arm 2 (Placebo): Matched placebo ^{CCI} at Week 0 and then ^{CCI} thereafter through the end of the total study period.

Randomization will be stratified by clinical remission status at baseline (CDAI < 150, CDAI \geq 150), region (North America, Western Europe, rest of world) and number of prior surgeries (1 surgery versus > 1 surgery, with the qualifying surgery counting as 1 surgery).

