5. 6.	Discontinuation of study intervention due to COVID-19 related reasons (excluding COVID-19 infection) Discontinuation of study intervention due to reasons other than those in ICE 3 or 5	and any data observed after the associated ICE event will be used for the analysis

Abbreviation: AE=adverse event; CD=Crohn's disease; COVID-19= Coronavirus disease 2019; ICE=intercurrent event

20

Intercurrent events in categories 1-4 will be handled by the composite strategy. The composite strategy assesses the treatment effects not only based on the variable measurements, but also based on ICEs. This estimand acknowledges that having an ICE in categories 1-4 is an unfavorable outcome. For participants experiencing ICEs in category 5 and 6, the treatment policy strategy will be used and considers the occurrence of ICE category 5 and 6 is irrelevant in defining the treatment effect and so observed values of the variable will be used, if available, regardless of the occurrence of ICE category 5 and 6.

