Time-to-event endpoints will be summarized with median survival time and interquartile range of survival time by treatment group. Kaplan-Meier curves will be provided for time-to-event endpoints as well. Treatment comparisons will be performed using the log-rank test stratified by clinical remission status at baseline (CDAI < 150, CDAI \ge 150), region (North America, Western Europe, rest of world) and number of prior surgeries (1 surgery versus > 1 surgery, with the qualifying surgery counting as 1 surgery).

Continuous Endpoints

The ICEs specified as following will be applied to each of the above continuous endpoints, ie, if a participant has an ICE in categories 1-4, last available values will be assigned from the point of ICE onward (i.e., no change from baseline). For participants experiencing an ICE 5 or ICE 6, their observed values will be used, if available. Note that the application of ICE categories 1-4 overrides that of ICE 6 and ICE 6. This means that for a participant with an ICE in categories 1-4 baseline values will be assigned from the point of ICE onward (ie, no change from baseline), regardless of whether the participant has had an ICE 5 or ICE 6.

To account for the missing data for continuous endpoints of change from baseline measured at more than one post-baseline visit (after applying the ICEs), a Mixed-Effect Model Repeated Measures (MMRM) will be used, under the assumption of missing at random (MAR), to test the difference between treatment groups. In MMRM, missing data will not be imputed, but rather missing data will be accounted for through correlation of repeated measures in the model. Additionally, if the MMRM normality assumption is in question, an appropriate transformation may be implemented before fitting the MMRM model.

The explanatory variables of the MMRM model will include treatment group, visit, applicable baseline score, clinical remission status at baseline (CDAI < 150, CDAI \ge 150), region (North America, Western Europe, rest of world) and number of prior surgeries (1 surgery versus > 1 surgery, with the qualifying surgery counting as 1 surgery), an interaction term of visit with treatment group, and an interaction term of visit with applicable baseline score.

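### After ICEs 1–4 the SAP gives continuous exploratory endpoints two incompatible values, and one of them replaces recorded worsening with zero

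*SAP*

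**What the plan says.** The text is in SAP Section 5.5.2, under Continuous Endpoints. For a participant with an ICE in categories 1–4 (CD-related surgery, prohibited CD medication change, discontinuation for lack of efficacy or worsening CD, cross over to open-label guselkumab), "last available values will be assigned from the point of ICE onward (i.e., no change from baseline". After the rule for ICEs 5 and 6 comes a precedence statement, "the application of ICE categories 1-4 overrides that of ICE 6 and ICE 6", which is explained by saying that for the same participants "baseline values will be assigned from the point of ICE onward (ie, no change from baseline".

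The endpoints concerned are those listed in SAP Section 5.5.1 as changes from baseline: PROMIS-Fatigue ("Change in PROMIS-Fatigue SF 7a at each post baseline visit through Week 152"), PROMIS-29, WPAI, CRP and fecal calprotectin. They are analysed by MMRM after the ICE rule has been applied.

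Elsewhere the SAP takes a clear position on the same events. For the primary estimand (Section 5.3.2.1): "This estimand acknowledges that having an ICE in categories 1-4 is an unfavorable outcome". For exploratory binary endpoints (Section 5.5.2): "Participants with ICEs in categories 1-4 will be considered to have unfavored outcome".

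**The concern.** Two different values are prescribed for the same participant at the same visits, and both are described as zero change. A programmer could implement either and cite the SAP for it, and the two data sets would estimate different quantities.

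The choice matters because of who is enrolled. Participants enter after resection "without evidence of active disease postoperatively", and "Participants will have a baseline CDAI <200" (SAP Section 1.2.1). The trial looks for deterioration from that state. In a trial that enrols active disease, returning a failure to baseline withholds credit for improvement. Here it withholds the record of getting worse, which sits badly with calling the event unfavourable.

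**Working it through.** **1. The two rules side by side.** Let Y0 be the baseline value and YL the last value available at the ICE.

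- Last-available rule: assigned change = YL − Y0.
- Baseline rule: assigned change = Y0 − Y0 = 0.

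They coincide only when YL = Y0. The zero-change gloss is therefore true of the baseline rule by construction, and of the last-available rule only in that special case.

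**2. Whether another text settles it.** Protocol Sections 9.4.2 and 9.4.3 give ICE strategies for the primary and the first two secondary endpoints. Section 9.4.4 gives none for continuous endpoints. SAP Appendix 2 is empty on the matter. LOCF is in the SAP abbreviation list, but no section assigns it to these endpoints. Nothing resolves the conflict.

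**3. Consistency with the binary rule.** Fecal calprotectin is analysed twice: as binary recurrence and as change from baseline. Under the baseline rule, a participant with an ICE in categories 1–4 counts as unfavourable on the first and as unchanged on the second.

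**4. Size.** The documents give no effect size, SD or power for any continuous endpoint, so there is no stated figure to reproduce. The following is an illustration with assumed inputs.

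- pP and pG are the shares with an ICE in categories 1–4 on placebo and guselkumab. The documents do not give them. Two proxies from SAP Section 3 are used: endoscopic recurrence (50% v 30%) and disease recurrence (20% v 10%).
- D is the mean last-available change in failures (positive = worse), the same in both arms.
- s is the mean change in everyone else, the same in both arms.

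Guselkumab minus placebo difference in mean change:

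- last-available rule: [pG×D + (1−pG)×s] − [pP×D + (1−pP)×s] = −(pP−pG)×(D−s)
- baseline rule: [(1−pG)×s] − [(1−pP)×s] = (pP−pG)×s
- last-available minus baseline: −(pP−pG)×D

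Example with 50% v 30%, D = 5, s = −5. Last available: (0.30×5 − 0.70×5) − (0.50×5 − 0.50×5) = −2.0 − 0 = −2.0. Baseline: (−0.70×5) − (−0.50×5) = −3.5 + 2.5 = −1.0.

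| Shares, placebo v guselkumab | s | D | Last available | Baseline |
|---|---|---|---|---|
| 50% v 30% | 0 | 1 / 5 / 10 | −0.2 / −1.0 / −2.0 | 0.0 |
| 50% v 30% | −5 | 1 / 5 / 10 | −1.2 / −2.0 / −3.0 | −1.0 |
| 20% v 10% | 0 | 1 / 5 / 10 | −0.1 / −0.5 / −1.0 | 0.0 |
| 20% v 10% | −5 | 1 / 5 / 10 | −0.6 / −1.0 / −1.5 | −0.5 |

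The recorded worsening removed by the baseline rule is (0.20−0.10)×D = 0.10×D to (0.50−0.30)×D = 0.20×D. Taking D = 100 µg/g for calprotectin, the rise in the SAP's own recurrence definition, gives 10 to 20 µg/g on the raw scale. The MMRM may be fitted to transformed data, so this is only a yardstick.

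**5. What the formulas do not give.** With s = 0 the baseline rule returns zero. With s below 0 it returns a difference in guselkumab's favour. The gap between the rules takes its sign from D: if failures' last value is still below a raised baseline, D is negative and the baseline rule scores them worse than recorded. There is no fixed direction.

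**6. Timing.** Mandatory cross over for endoscopic recurrence follows the Week 48–51 ileocolonoscopy, so the 50% v 30% proxy bears mainly on visits after Week 48. Earlier, cross over comes from disease recurrence or, at discretion, the optional Week 24 endoscopy. The 20% v 10% proxy, itself planned over all follow-up to the main lock, is then the closer one.

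**The case against.** The likely intent is baseline carried forward. Both glosses describe zero change, and the sentence assigning baseline values is written as an explanation. That is a fair guess, but the first sentence says something else and no reason is given for a neutral value.

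A reader might go further and infer that zero change is close to the best result a failure could receive, so that these comparisons are always biased towards the null. The documents do not support that. Baseline is Week 0, about 10 to 49 days after resection (Protocol Section 5.1, criterion 3). Protocol Section 4.3 notes that calprotectin can stay mildly raised for up to three months after surgery and that CRP can also be raised. Early fatigue and work impairment are plausible too (assumption). If other participants improve from such a baseline, zero change is worse than their outcome. The 50% v 30% figures are also endoscopic recurrence rates, not ICE rates, so 0.20×D is the upper end of the illustrated range and not an estimate.

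Nor is the last-available rule free of faults. PROMIS and WPAI are scheduled at Weeks 0, 8, 24, 48, 80, 128 and 152 and not at the flare visit, so for surgery or a medication change (ICEs 1 and 2) the last score may precede the deterioration by months. This caveat stands. The rule does better at cross over, where CRP, calprotectin, PROMIS and WPAI are scheduled before dosing.

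Worsening is also not wholly hidden: calprotectin recurrence is analysed separately with these ICEs counted as unfavourable. Finally, all six ranked endpoints are binary or time-to-event (SAP Section 5.4.1.3), and the continuous endpoints are exploratory with nominal p-values. SAP Section 1 says that four subjects were enrolled and keeps the planned analyses for reference only. These limits are accepted and set the severity.

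**Conclusion.** The contradiction is real and follows from the text alone. The baseline reading also discards recorded worsening for events that the SAP calls unfavourable. Its cost is 0.10×D to 0.20×D in the difference in means, provided that failures worsen by D equally in both arms, that others do not change, and that ICE shares lie between 20% v 10% and 50% v 30%. None of these is given in the documents, and neither a general bias to the null nor a near-best score for failures is established.

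Severity is minor. Only exploratory continuous endpoints are touched, the primary and ranked secondary analyses are unaffected, and this trial's reported results do not change because the planned comparisons will not be run. The point matters for the plan as written and for any reuse of it.

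**What to change.** In SAP Section 5.5.2, Continuous Endpoints:

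- State one rule. The last value observed on or before the ICE is preferred, because it keeps worsening already recorded, including the pre-dose assessments at the cross over visit. Say openly that for ICEs 1 and 2 the last patient-reported score may predate the deterioration.
- Delete the zero-change gloss and the sentence assigning baseline values.
- In the precedence statement, correct the repeated ICE 6 to ICE 5 and ICE 6.
- Add an MMRM on the data as observed, regardless of ICEs 1–4, as a sensitivity check. It would include values after open-label treatment and should be labelled so. Cross over visits are timed from cross over, so their mapping to analysis visits has to be stated.

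The cost is a few lines of SAP wording and one extra model per endpoint. No new data are needed.
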